## **A. SPECIFIC AIMS**

Dental practices have advanced tobacco cessation by adopting a model of brief advice similar to that used by medical providers. We propose a randomized clinical trial designed to allow dental hygienists to provide additional tobacco cessation counseling with little additional marginal effort. This would be done using an internet-based referral to external resources. This system, termed "Refer2Quit", will allow hygienists to refer patients to a patient education website and accompanying Quitline, while the patient is still in the dental office. Our overall goal is to advance science related to internet use in health services delivery by targeting dental hygienists. The intervention will also support subsequent brief counseling by providing feedback on the activities of patients to the practice through a secure server.

We have these specific aims:

- (1) To test the hypothesis that the proportion of patients **REFERRED** to self-management resource websites will be larger in intervention practices compared to control practices. We expect to observe a referral rate of 24% among intervention practices compared to the 12% observed from protocols similar to the control practices.
- (2) To test the hypothesis that the proportion of patients referred who **GO** to the patient self-management website will be larger in intervention practices (40%) compared to control practices (20%).
- (3) To test the hypothesis that the proportion of smokers who are referred who **QUIT** at six months will be larger among intervention (15%) compared to control (10%) because of the additional connectivity of the intervention.

This will be done by randomizing 80 (40 per arm) community-based dental practices into a clinical trial that contrasts the intervention with a paper-based "information prescription".

The intervention is a multi-component internet-delivered clinical microsystem intervention using: (1) "Refer2Quit", a point-of-care "patient referral portal" that hygienists can use to enroll patients into a self-management system; and (2) "Decide2Quit", a patient self-management portal organizing interactive, tailored, patient education and cessation planning links to other high-quality web (smokefree.gov) and offline resources (1-800-QUIT-NOW).

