interviews. However, these delayed reports of provider performance may suffer from recall bias due to time elapsed from the patient visit to the time of follow-up assessment. Immediate exit interviews for smoking cessation have been found to correlate with audiotapes.

In DTC.Net, we have developed and evaluated patient-reported provider performance measures that are completed and collected and the time of the visit on “Exit Cards.” These patient Exit Cards – brief surveys completed by patients at the end of their appointment – were developed using principles of ecological momentary assessment (EMA). EMA is a method used in health behavior and more recently in health services research to overcome limitations of traditional self-report assessments.

Practices will be provided a set of 100 patient exit cards at each assessment interval. As a baseline, practices will be provided 50 cards in the run-in phase. At each practice, exit cards will be distributed by office staff to consecutive patients (19 and over). Eligible patients will be adults who have completed their visit. In a pilot study for DTC.Net, patients were asked to record the time required to complete the pilot survey. The average time to complete was two minutes and ranged from one to three. The exit cards are administered while the patient is awaiting follow-up instructions and completing payment. A brief statement is included explaining the study, indicating that participation is voluntary, and that their responses will not influence the care that they receive. Importantly, participation is anonymous and no patient identifiers will be included on the Exit Cards. This recruitment is solely to assess provider performance and no patient follow-up is needed.

Each patient is provided a pen to help complete the survey and as a gift. Patients place completed exit cards in an accompanying envelope and then deposit in a sealed collection box. If a patient is not interested in completing the exit card, they write “declined” and return the card to the box. When all exit cards are distributed, the practice returns the collection box to our coordinating center. For each set of 100 exit cards, we estimate 20 to 25 tobacco users will be identified.

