**D8. Main Evaluation Measures**

As depicted in Figure 4, HI-QUIT is designed to have a sequence of effects on the process of care within each clinical microsystem. Thus, we have designed our main evaluation to assess several key areas of influence that we have abbreviated as **Refer -> GO -> QUIT**. For our hypotheses, we have three primary dependent variables. Each of the outcomes is collected at the patient level and is used to create a proportion. The first link in the chain of evaluation is of course to assess the performance of the provider. We will use the exit cards to assess the proportion of smokers who are referred. This is assessed at discrete time points (Patients recruited in 3 cohorts at intervention Time 0 (I0) (pre-intervention), I0 + 6 months, I0 + 12 months,).

This analysis is solely to assess provider performance and data are collected from patients anonymously. The proportion of smokers who are referred who GO to the website (H2), and the subsequent

Table 10: Dependent (outcome) variables (Refer -> GO -> QUIT)					
Label	Question	Source	Collected	Numerator	Denominator
Refer (H1)	During your provider’s visit TODAY did anyone: Refer you to Decide2Quit* - a website with information about tobacco?	Patient Exit Card	Discrete Intervals (baseline, 6 and 12 Months)	Number Referred	Number of Smokers
GO (H2)	Proportion of patients from the practice who log onto website	Website tracking and information prescriptions	Continuous	Number who GO	Number Referred ‡
QUIT (H3)	Do you currently smoke cigarettes (smoked even 1 puff in the last 7 days)?	6 month survey†	Continuous	Number who QUIT	Number Referred ‡
* control website for Controls; † validated using mailed cotinine saliva kit. ‡ Assessed by web tracking in intervention, in control by leave-behind receipts from information prescriptions					

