providers and patients. Thus, our analysis should be designed to evaluate these sources. To this end we will use multilevel modeling to explicitly evaluate the sources of variability in HI-QUIT usage.

Analyses for H1: We will assess differences between intervention and control in three ways.

As our **primary analysis**, we will use patient-level data and multilevel modeling to account for practice-level effects and adjusting for the complex effects of patient and provider variables in multivariable analyses. We have chosen this as the primary analysis for two reasons: 1) because this analysis represents a detailed understanding of the effects of the clinical microsystem intervention, and 2) because we have empirically-driven intraclass correlation coefficients to guide our power calculations.

Thus, to test the overall effect of HI-QUIT, we will use data from all post-intervention evaluation time points together. The hypothesis will be tested by using logistic regression, using patient-level data and incorporating practice-membership as a design factor. An important consideration in handling correlated data resulting from group-randomization is properly accounting for the correlations in the analysis. For example, positive correlations will result in the underestimation of standard errors of the between-practice effects and overestimation of the standard errors of the within-subject effects. Generalized Estimating Equations (GEE), specifically designed for correlated outcomes that can be modeled with a generalized linear model (GLM) including logistic regression, will be used. PROC GENMOD can easily accommodate GEE methods adjusting for clustering. For multivariable analyses logistic regression will be used again, with accounting for clustering. These models will allow adjustment for patient and practice variables described in Section D7. We will also test the hypothesis using data from each individual time point.

**Hypothesis 2: The proportion of patients referred who GO to the patient self-management website will be larger in HI-QUIT practices (40%) compared to control practices (20%).**

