- 2) We assume that only two providers per practice will be actively involved in referring patients. Thus, for some practices more providers may participate and the number of patients referred (say if four hygienists and dental assistants refer) may be considerably greater.

**Hypothesis 1:** This analysis will test whether HI-QUIT practices refer patients at a higher rate than control practices. The literature supports estimating the mean baseline referral rate of 12% for control practices.

Power was estimated using a two-sided chi-square test for a difference in proportions with a Type 1 error rate of 0.05. To take a conservative approach, power was calculated assuming an average of 66 smokers per practice responding to the exit cards. Due to

H1: Number of subjects needed per group for 80% power with a two-sided $\chi^2$ test of equal proportions and $\alpha=0.05$ , adjusting for clustering in practices				
	1	2	3	4
Control proportion, $\pi_1$	0.12	0.12	0.12	0.12
HI-QUIT proportion, $\pi_2$	0.24	0.22	0.20	0.19
Unadjusted n needed per group	176	240	354	447
Adjusted n needed per group*	1,892	2,580	2,805	4805
Number of practices needed per group	29	39	58	73

\* Design factor (  $D = [1 + (m-1) r]$ ) inflates n to account for clustering

clustering within practices and clustering within providers, these will not all be independent observations. The standard practice is to adjust the sample size by an inflation factor  $D = [1 + (m-1) r]$  where r is the intra-class (practice-level) correlation (ICC) and m is the number of subjects per group (practice). Pilot data from DTC.Net revealed a relatively large ICC of 0.15 for rates of advice to quit smoking within dental practices. Assuming equal ICCs of 0.15 for Refer and a cluster size of 66 smokers per practice gives  $D= 10.75$ , or an effective sample size per practice of approximately 6 patients. With these numbers only 29 practices per arm are required to achieve 80% power to detect a significant difference in referral rates of 0.12.

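### The baseline Refer item asks about a study website that practices cannot yet refer to, and the H1 test names no practice-level baseline term, so H1 gives up precision at no saving

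*Protocol*

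**What the plan says.** **Timing and content of the cards.** D6 (Exit Card Surveys) gives each practice 100 cards per assessment interval. For the run-in it states: "As a baseline, practices will be provided 50 cards in the run-in phase". It expects 20 to 25 tobacco users per 100 cards. The card also records age, gender, the other 5A components and stage of change.

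**The Refer item.** Table 10 (D8) lists Refer as collected at baseline, 6 and 12 months. The one wording given asks whether anyone at the visit did this: "Refer you to Decide2Quit* - a website with information about tobacco". A footnote substitutes the control website in control practices. D5, step 5, has providers reach the website and begin referring once the run-in is complete. Randomisation follows when the first provider agrees online.

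**The H1 test.** The outcome is Refer at 6 and 12 months. For the overall effect, "we will use data from all post-intervention evaluation time points together", by logistic regression with GEE for clustering. The primary-analysis paragraph speaks in general terms of adjusting for patient and provider variables. On the multivariable models it says: "These models will allow adjustment for patient and practice variables described in Section D7". Table 9, in D7, marks pre-intervention tobacco counseling from the exit cards as a baseline covariate.

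**H1 power (D10).** "Power was estimated using a two-sided chi-square test for a difference in proportions with a Type 1 error rate of 0.05". The assumptions are 12% v 24%, ICC 0.15 (the ADVISE figure from the predecessor trial) and 66 smokers per practice.

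**The concern.** In a practice-randomised trial with ICC 0.15, most of the error in the arm comparison lies between practices. D10 makes this plain: 66 smokers per practice count as about 6. More cards per practice help little, whereas a baseline measure that predicts a practice's later referral rate removes part of that error directly.

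The trial already pays for such a measure, and two choices weaken it:

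- The run-in Refer item names a site that the practice cannot yet refer to. An item that is near zero everywhere has almost no between-practice variation, so it can explain nothing at follow-up. A rise from it to 12 months would reflect only the arrival of the study materials. It also says nothing about usual referral, although D10 states: "The literature supports estimating the mean baseline referral rate of 12% for control practices".
- The run-in cards do hold usable items, ADVISE among them, but the primary H1 model does not commit to any of them.

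A later analysis plan can name covariates. It cannot repair an item already collected with the wrong wording, so the time to act is before the run-in cards are printed.

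**Working it through.** **1. Reproduce the plan's figure.** Inputs from D10: 12% v 24%, two-sided 0.05, 80% power, ICC 0.15, m = 66.

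- Unadjusted n per arm with continuity correction: 176 (160 without). The plan's 176 is therefore a continuity-corrected figure.
- D = 1 + (66 − 1) × 0.15 = 10.75, and 176 × 10.75 = 1,892.
- 1,892 / 66 = 28.7, so 29 practices per arm. All three stated figures reproduce.

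**2. Smokers per practice available to the test.** At 20 tobacco users per 100 cards, the 6- and 12-month rounds give 2 × 20 = 40, and the 50 run-in cards give 10. These replace 66 below. The change is small because the ICC dominates: D = 1 + 39 × 0.15 = 6.85, and 40 / 6.85 = 5.84 effective smokers per practice, against 66 / 10.75 = 6.14.

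**3. Power without a baseline term.** Effective n per arm is 30 × 5.84 = 175.2 or 40 × 5.84 = 233.6. Continuity-corrected power:

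| Contrast | 30 per arm | 40 per arm |
|---|---|---|
| 24% v 12% | 80% | 91% |
| 22% v 12% | 65% | 79% |

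The range of 30 to 40 completing practices per arm is the protocol's own (D5, Anticipating attrition). The 22% alternative is the second column of the H1 table.

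**4. What a baseline practice rate could remove.** The reliability of a practice mean is m × ICC / (1 + (m − 1) × ICC).

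- Run-in, m = 10: 1.5 / 2.35 = 0.638.
- Follow-up, m = 40: 6 / 6.85 = 0.876.
- Share of variance removed: R² = c² × 0.638 × 0.876 = 0.559 c², where c is the correlation of true practice effects between baseline and follow-up.
- Equivalent practices: 30 / (1 − R²).

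The protocol gives no value for c, so a range is shown for 30 practices per arm.

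| c (assumed) | R² | 30 practices act like | Power, 24% v 12% | Power, 22% v 12% |
|---|---|---|---|---|
| no adjustment | 0 | 30 | 80% | 65% |
| 0.3 | 5% | 32 | 82% | 68% |
| 0.5 | 14% | 35 | 86% | 73% |
| 0.7 | 27% | 41 | 91% | 80% |

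**5. The item as worded.** If baseline Refer is near zero in every practice, its between-practice variance is near zero and so is R². The gain from using it is about nil.

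**The case against.** The strongest reply is that nothing here is invalid. Practices are randomised, so comparing post-intervention cards alone is unbiased, and H1 uses baseline Refer neither as an outcome nor as a named covariate. A near-zero baseline spoils no planned test. The exact covariate list is commonly left to the statistical analysis plan, and the primary-analysis paragraph already speaks of adjusting for patient and provider variables. All of this stands, and it limits the point to efficiency.

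Four stronger readings are tempting, and the documents do not support them:

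- *The run-in data cannot help H1.* The cards also record other 5A items, Table 9 lists pre-intervention counseling as a baseline covariate, and the H1 models allow adjustment for D7 variables. Only the Refer item is close to empty.
- *Every baseline answer must be no.* D5 implies that answers will be near zero. It does not rule out a stray yes, and the control site was built and tested before this trial.
- *H1 is underpowered.* At the hypothesised 24% v 12% it has about 80% power even at the lower completion figure.
- *H1 is always the weakest hypothesis.* D10 asks for 29 practices per arm for H1, against 10 for H2 and 8 for H3. That ranking belongs to the base case: if only 30% of referred intervention smokers go to the site, D10 asks for 36 for H3.

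It is also fair that the size of the gain rests on an assumed correlation. At 0.3 the gain is only 2 to 3 percentage points.

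**Conclusion.** The point holds as an avoidable loss of efficiency. The baseline Refer item, as worded, will carry almost no information, and the primary H1 model fixes no practice-level baseline term although suitable run-in data are collected. There is no bias and the planned test is not invalid.

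At 30 practices per arm, the power at stake is about 2 to 12 percentage points for 24% v 12% and 3 to 15 for 22% v 12%, over assumed correlations of 0.3 to 0.7. At 40 per arm the 24% contrast already has 91%, so less is at stake there.

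These figures rest on 10 run-in and 40 follow-up smokers per practice, ICC 0.15 at both times, the continuity-corrected basis of D10, and a variance reduction worked on the scale of practice proportions. If the covariate is ADVISE rather than general referral, the relevant correlation is between baseline ADVISE and later Refer, for which the protocol has no figure.

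**What to change.** 1. **Run-in card.** Replace the study-site question with one on referral to any quit-smoking website, quitline or programme. Keep the study-site item for the 6- and 12-month cards as the H1 outcome. Amend the Refer row of Table 10 so that baseline and follow-up items are shown separately.
2. **Analyses for H1.** State that the primary GEE model adjusts for the practice-level run-in referral rate, the run-in ADVISE rate, or both, and fix the choice before follow-up data are seen. ADVISE is a sensible safeguard if general referral also proves rare: in the predecessor trial its pre-intervention rates were 44% and 42%, with ICC 0.15.

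The cost is one line on the card, one sentence in the plan, and one or two degrees of freedom among 60 to 80 practices. No extra cards or practices are needed.

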**Figure 3: Timeline for Intervention Development, Implementation, and Evaluation**

Study Months	Development						Intervention and Evaluation																													
	Year 1						Year 2												Year 3																	
	1	2	3	4	5	6	7	8	9	10	11	12	13	14	15	16	17	18	19	20	21	22	23	24	26	28	30	32	34	36						
Formative research	█																																			
Develop Content	█																																			
Program Website	█																																			
Test Usability	█																																			
Activate HI-QUIT							X																													
Enroll Practices	█																																			
HI-QUIT Available*	█																																			
Patient Exit Cards (H1) †							█						█																							
Web Activity (patient/provider) (H2)							█						█																							
Patient Telephone Follow-up (H3) ‡							█						█																							
End of Project Surveys and Qualitative Interviews																									█											
Hypothesis Testing, Manuscripts	█																																			

\* Available for 21 months for each practice, with monthly updates  
 † Patients recruited in 3 cohorts at Intervention Time 0 (I0), I0 + 6 months, I0 + 12 months  
 ‡ Telephone Follow-up: Tobacco users from website – cessation assessed at 6 months (with cotinine validation)

Although HI-QUIT is heavily focused on enhancing Refer, the intervention has the potential for impact across the 5As. To further clarify, Figure 4 depicts flow of a single example practice and patient over time.

**Figure 4: How HI-QUIT will improve processes of care (5As) and increase smoking cessation – use of the clinical microsystem intervention over time by One example practice and One patient.**

- A1: ASK** – Refer2Quit sends email prompts to hygienists reminding them of the importance of smoking cessation, hygienist downloads printable chart stickers, etc. to increase systematic screening.
- A2: ADVISE** – Refer2Quit materials provide additional knowledge to hygienist on strong advice, dentist/hygienist advises patient.
- A3: ASSESS** – Hygienist explains content of Decide2Quit and assesses willingness of patient to use system, and to Quit.
- A4: ASSIST** – Patient agrees to be recruited and hygienist uses Refer2Quit to directly refer. Decide2Quit sends email reminders to the patient. Patient uses system and talks to family because of the motivational messages.

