### 1. Hygienists’ Portal - Refer2Quit:

The core of the Refer2Quit hygienist portal is a Secure Sockets Layer (SSL) encrypted web form where providers can enter patient’s emails into the system if they agree to be referred. Although we anticipate that hygienists will drive this intervention, dentists will also be able to access the intervention website. The form will be designed to be easily completed by hygienists or front office staff as the patient is discharged from the visit. The Refer2Quit component is targeted to providers. To maximize the use of Refer2Quit, we will supplement the component with supportive sub-modules designed to prompt providers to use the system and maximize their smoking cessation activities.

The Practice Toolbox is patterned after a series of successful Internet-delivered provider interventions including [name] previous Chlamydia Screening intervention, and more so, the current DTC.Net intervention (see Appendix A). Reviewers can access this current website at [www.oralcancerprevention.org](http://www.oralcancerprevention.org). To login, you will be asked to enter a first and last name, use firstname = nih and lastname = reviewer.

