### D3. The CONTROL – information prescriptions to refer to patients

#### 1. Hygienist Control – Information Prescriptions

In planning this proposal, we considered several potential controls as suggested by the framework for evaluating complex

interventions. In DTC.Net, we are currently using a wait-list control group. Control providers will have access to the full intervention after data collection is complete. Thus, control hygienists are delivering “usual care.” However, for this intervention, we felt that a wait-list control ignores other recent advances in provider referrals to self-management in smoking cessation (i.e.: information prescriptions).

Also, although we have not had differential attrition in the wait-list control, compared with intervention, in DTC.Net, anecdotally, control providers have expressed concerns about having “nothing new” to provide to patients. We are concerned about the threat of long-term wait-listing to overall retention in the control group. Specifically, we want to test the uniqueness of the integration clinical microsystem intervention. After consideration, we have chosen a more active, symmetric control reflecting recent offline research into provider referrals. Thus, our control group provides parallel interventions – for providers and then patients – that are *not* integrated.

We have chosen an “information prescription” control. Providers in the control group will be provided preprinted pads of “information prescriptions” with their office information, motivational messages for patients, a space for the provider to sign, and the control website address.

The information prescription pads also have an important role in our analysis. The pads will have numbered leave-behind receipts used to tally the number of referrals issued. These pads will be collected from the control practices to obtain an accurate account of the number of patients referred. The control group will not have access to 1) HI-QUIT Help Desk, 2) Refer2Quit portal at the point of care; 2) Feedback Reports of patient activity; 4) automated email reminders for patients and providers; 5) HI-QUIT content updates and linking functions.

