proportion who QUIT (H3) are assessed continuously throughout the study. For H2, the numerator is the number who GO, as tracked by HI-QUIT and the control website. The denominator is the number referred. Because of the nature of the Internet versus paper referral system, by definition, the continuous assessment of the number of patients who are referred is different by study arm. Our interest in H2 is the proportion of patients referred who logon, or ‘GO’, to the website (% who go = number who visit/number referred). In the intervention group, the webserver collects the number of patients entered into the system per practice (i.e.: denominator, the number referred). In the control group, patients are not entered into an electronic system, but are referred using an “information prescription.” In both groups, the intervention and control websites collect the number of patients who visit the site. Thus, assessment of the numerator is the same, but assessment of the denominator is systematically different by arm. We have developed protocol for more accurately measuring the denominator and the number referred in the control group by using the information prescription pads with a leave-behind notation of when the patient was referred. We will collect the empty prescription pads from the control practices to assess the number of patients referred for the denominator.

For H3, the dependent variable is point prevalent cessation (QUIT). Smoking cessation trialists have recommended assessment of smoking cessation in randomized trials using both measures of 1) point

Principal Investigator/Program Director (Last, First, Middle): DPBRN c/o [name]

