Secondary analysis: Our primary approach does have the potential for errors resulting from lost, damaged, or mis-used “information prescription” pads in the control. This would result in a differential misclassification in the control as compared to the intervention group. As much of this error would underestimate the control denominator, it would still provide a conservative estimate. However, it is true that the inherent difference in the intervention and control creates a difference in the assessment of the denominator. Thus, as a secondary analysis and as safeguard against these error sources, we will repeat the analysis using the number of patients who GO as the outcome, with careful adjustment for *patient volume, proportion of smokers, and rates of referral as assessed by the exit cards at discrete time points*. This will allow us to check for consistency of results. The secondary analysis for the number who GO will use linear regression to model the number of patients per practice who go to the website by treatment assignment adjusted as above, where the test of H2 will be the significance of the coefficient for treatment assignment.

**Hypothesis 3: The proportion of smokers who are referred who QUIT at six months will be larger among intervention compared with control because of the additional connectivity of HI-QUIT.**

Data Definitions for H3: The main dependent variable for H3 is the dichotomous outcome of patient tobacco cessation (quit). The primary independent variable is assignment to intervention or control group. We have designed a patient-level analysis around point prevalence cessation based on the following question: “Do you currently smoke cigarettes (smoked even 1 puff in the last 7 days)?”

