**Hypothesis 2:** This analysis will test the proportion of patients referred who GO to the website, comparing HI-QUIT practices and control practices. As discussed above, a conservative base rate for control practices is for 12% of smokers to be referred and for approximately 20% of those to GO to the website. We expect these proportions to increase for the intervention group to 24% and 40%, respectively. We then need to examine statistical power to detect a 20% difference (40%-20%) in the proportion of referred patients who GO between the two groups, which corresponds to an odds ratio of 2.8. Based on approximately 200 smokers per practice per year and the referral rates above, we expect averages of 24 and 48 smokers to be referred from each control and intervention practice, respectively (Table 8).

Because of the group randomization, our effective sample size must again be reduced by a design factor for each group. Because "GO" to the website is more patient-directed, we have assumed a lower ICC of 0.05 for this analysis. Conservatively assuming an ICC of 0.05, we calculated design factors of 2.2 and 3.6 for the control and intervention groups, respectively. Incorporating the design factors gives an effective sample size per practice of 12 for the control group and 14 for the intervention group. Using a two-sided chi-square test with Type 1 error rate of 0.05, only 10 practices per arm are required to achieve 80% power. If we assume a smaller effect where only 30% of referred smoker in the intervention group GO, 30 intervention practices and 30 control practices are sufficient to achieve 80% power.

**Hypothesis 3:** This analysis of patient cessation outcomes is again conducted at the patient level. As detailed in the analysis plan we will approach this hypothesis in two ways and power calculations will be presented for each. For both approaches, this hypothesis will be tested as a two-sided chi-square test for equality of proportions and the number who quit will be assessed at follow-up among those who visited the website.

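### H2 and H3 count referred patients differently by arm, and the claim that the H2 error is conservative covers only lost or damaged control receipts

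*Protocol*

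**What the plan says.** **Intervention denominator.** D2, item 1, has providers enter patients' "emails into the system if they agree to be referred". Figure 4, step A4, gives the same order of events: "Patient agrees to be recruited and hygienist uses Refer2Quit to directly refer". D8 then takes the number entered into the web system as the number referred.

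**Control denominator.** D3, item 1, supplies pads with "numbered leave-behind receipts used to tally the number of referrals issued". No agreement or e-mail condition is stated.

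**Where it applies.** Table 10 puts the same footnote on the GO (H2) and QUIT (H3) denominators. The H3 text in D9 instead says that it shares the H1 denominator, which Table 10 gives as the number of smokers.

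**What the plan says about the difference.** D8 concedes that "assessment of the denominator is systematically different by arm". D9 (Analysis for H2) nevertheless says the receipts allow an exact proportion. The secondary-analysis paragraph names lost, damaged or mis-used pads and concludes: "As much of this error would underestimate the control denominator, it would still provide a conservative estimate". It then acknowledges the inherent difference between arms and adds a safeguard, which "will use linear regression to model the number of patients per practice who go to the website by treatment assignment", adjusted for patient volume, proportion of smokers and exit-card referral rate.

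**Opposite selection.** Under H3, D9 expects that control practices may refer mainly smokers who are ready to change, while intervention practices refer less selectively. It adjusts for readiness as entered on the website.

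**The concern.** Patients who decline, or who have no e-mail to give, are probably the least likely to visit a website. They drop out of the intervention denominator but stay in the control denominator if handed a slip. The intervention proportion can then exceed the control proportion when the systems do not differ in how many offered smokers they bring to the site.

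The plan's reasoning on direction concerns the control pads only. It never names the agreement filter as a source of bias. H3 inherits the same denominators, and its readiness adjustment cannot repair them, because a referred patient who never logs on never enters readiness. What is at stake is whether a significant H2 result can be read as an effect of the system, and whether a reader should trust that the error runs in the safe direction.

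**Working it through.** **1. The plan's own figures.** Table 8 reproduces: 200 smokers × 24% = 48 referred and 48 × 40% = 19.2 who GO (intervention); 200 × 12% = 24 and 24 × 20% = 4.8 (control). For H2, D10 states: "Using a two-sided chi-square test with Type 1 error rate of 0.05, only 10 practices per arm are required to achieve 80% power". For 20% v 40%, the pooled-variance formula gives 82 per arm (91 with continuity correction). Divided by the stated effective 12 per control practice, that is 7 practices (8 with correction), not 10; ten give about 94% power. The difference is on the safe side and does not affect this point.

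**2. Inputs.** From D10: ICC 0.05; 24 and 48 referred per practice; two-sided α 0.05. From D5: 40 practices per arm randomised, 30 to 40 expected to complete. Design factors are 1 + 23 × 0.05 = 2.15 and 1 + 47 × 0.05 = 3.35 (D10 states 2.2 and 3.6). The effective numbers per practice are 24/2.15 = 11.16 and 48/3.35 = 14.33.

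Assumed, because the protocol gives no figure: *a*, the share of offered intervention smokers who agree and are entered; *r0*, the GO rate that decliners would have had.

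**3. Observed intervention GO with no true effect.** If 20% of all offered smokers would GO, then 0.20 = a × p + (1 − a) × r0, so

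p = [0.20 − (1 − a) × r0] / a.

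This leaves visits by patients not entered in Refer2Quit out of the numerator.

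**4. Chance of a significant H2 result favouring the intervention** (nominal 2.5% in that direction). Worked case: a = 0.8, r0 = 0, 40 practices per arm. Effective sizes are 40 × 11.16 = 446.5 and 40 × 14.33 = 573.1; pooled proportion 0.2281; null SE 0.02649; alternative SE 0.02618. Then Φ[(0.05 − 1.96 × 0.02649)/0.02618] = Φ(−0.073) = 0.47.

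| a | p, r0 = 0 | false positive, 40 / 30 practices per arm | p, r0 = 10% | false positive, 40 / 30 practices per arm |
|---|---|---|---|---|
| 0.9 | 22.2% | 13% / 11% | 21.1% | 6% / 6% |
| 0.8 | 25.0% | 47% / 37% | 22.5% | 16% / 13% |
| 0.7 | 28.6% | 89% / 78% | 24.3% | 37% / 29% |
| 0.5 | 40.0% | near 100% / near 100% | 30.0% | 96% / 89% |

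**5. What produces the full 40% v 20%.** Solving p = 0.40 gives a = (0.20 − r0)/(0.40 − r0): 0.50 at r0 = 0, 0.43 at r0 = 5%, 0.33 at r0 = 10%.

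**6. H3.** With r0 = 0, the control rate of 2% appears as 2%/a in the intervention arm: 2.5% at a = 0.8, 4% at 0.5, and the planned 6% only at a = 1/3.

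**7. Direction of the pad errors.** Losing 10%, 20% or 50% of receipts raises control GO to 0.20/0.9 = 22%, 0.20/0.8 = 25% or 0.20/0.5 = 40%, which is conservative, as the plan says. Over-counting slips by 10% or 20% lowers it to 0.20/1.1 = 18% or 0.20/1.2 = 17%, which is not. With r0 = 0, a receipt loss of 1 − a would exactly cancel the agreement effect.

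**The case against.** The plan is open about the difference. D8 states it, and D9 repeats it directly after the sentence on direction and adds a check that avoids the referral denominator. That sentence is hedged, refers to pad errors, and is correct for lost or damaged receipts. A reader might infer that the claimed direction is reversed; the text does not support that. It is incomplete. Mis-used pads are also named, although their direction is not worked out.

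A reader might also infer that the safeguard must fail, because equal 20% GO rates with the planned referral volumes give 48 × 0.20 = 9.6 v 24 × 0.20 = 4.8 visits per practice. That contrast is unadjusted, and the planned model adjusts for the exit-card referral rate. If offers were equal at 24 per practice and there were no true effect, both arms would show 24 × 0.20 = 4.8 visits, and the check would expose the artefact. What stands against the safeguard is narrower: it is only secondary, it fits a linear model to counts, and it adjusts additively for quantities that multiply.

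Finally, the selection described under H3, and any loss of receipts, work against the agreement filter. A flat statement that H2 and H3 are biased towards the intervention goes beyond the documents. This part of the objection stands, but an unknown net direction equally undercuts the word conservative.

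**Conclusion.** The point holds in limited form. The referred denominator means agreed and entered in one arm and slip issued in the other, for both H2 and H3. The conservative statement is valid for lost or damaged receipts only. The agreement filter pushes towards the intervention, other selection may push back, and the net bias is unknown, so the primary H2 estimate is neither conservative nor exact.

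The size rests on two figures that the protocol does not give. At 80% agreement and 40 practices per arm, the false-significance chance is about 47% if decliners never visit and about 16% if 10% would. At 90% agreement it is about 13% or 6%. A reader might conclude that the whole H2 effect is an artefact. That needs agreement of about 33% to 50%, which nothing in the protocol supports or rules out; at 80% to 90%, with decliners never visiting, only 2 to 5 of the 20 points arise. For H3, the denominator alone gives 6% v 2% only if a third agree.

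**What to change.** 1. **Text of D9.** Limit the conservative statement to lost or damaged receipts. State that over-counted slips and the agreement filter act in the opposite direction. Remove the claim of an exact proportion. Reconcile the H3 sentence on sharing the H1 denominator with Table 10.

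2. **One definition of referred in both arms, for H2 and H3.** Add to Refer2Quit an entry for a patient who was referred but declined or had no e-mail, and count these patients in the denominator. State also how a control patient who refuses the slip is tallied. The cost is a few seconds of data entry, in a portal that D4 wants kept minimal. Hygienists may under-log refusals, which would bring the bias back; logged totals can be checked against exit-card referral rates. Refusals that are not logged cannot be recovered later.

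3. **Secondary count analysis.** Replace the linear regression with a negative binomial or GEE Poisson model of GO per practice, with log offset = patient volume × smoker proportion, measured the same way in both arms. This estimates visits per smoker seen, so it includes any difference in referral and is a consistency check, not a substitute for the H2 proportion. Enter the exit-card referral rate, if used, as a covariate or a smoothed estimate. As a raw log offset it is undefined for practices with no reported referral. At the planned 12% rate and ICC 0.15, a beta-binomial (α = 0.12 × (1/0.15 − 1) = 0.68, β = 0.88 × (1/0.15 − 1) = 4.99) puts about 21% of control practices at zero with 44 carded smokers and 16% with 66. D10 uses 66; 44 is two rounds of 22. Exit-card estimates also add some variance.

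4. **H3.** Report the same per-smoker check for quits.
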